#### Adherence to inspiratory muscle training

The success of IMT will be defined by the adherence of participants to the intervention.

New variable	Rules
IMT adherence	
 
YES:
 
>= 1 IMT session initiated on >= 5 days / week during >= 2 weeks after randomisation AND
 
>= 30 breaths overall completed on each day
 

	
 
< 1 IMT session initiated on >= 5 days / week during >= 2 weeks after randomisation OR
 
>= 1 IMT session initiated on < 5 days / week during >= 2 weeks after randomisation OR
 
>= 1 IMT session initiated on >= 5 days / week during < 2 weeks after randomisation OR
 
>= 30 breaths overall completed on each day
 

	MISSING: otherwise

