#### 5.2.6 Main study (Phase 2)

Progression criteria from Phase 1 to Phase 2:

- all centres participating in the pilot are recruiting (in one or more specialties);
- at least 40% of eligible patients are consenting to randomisation;
- each centre recruiting >8 patients/month (from any specialty);
- interventions are delivered according to the protocol in all centres;
- the allocated intervention is initiated in >=90% of randomised participants;
- >=70% of patients randomised to high resistance IMT or low IMT adhere to allocated interventions (adherence will be recorded electronically by the IMT device); we will define a patient as adherent with the intervention if they use the IMT device at least five days a week (for a minimum of 30 breaths per day).

If progression criteria are met, recruitment will continue at the Phase 1 hospitals and we will begin recruitment at a minimum of an additional two hospitals (depending on how recruitment is going in Phase 1). Delivery mode of the intervention will be based on the findings in Phase 1 and any amendments to the study will be submitted for approval by the regulatory authorities.

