# 6.4 Duration of treatment period

The duration of the treatment commences when the participant receives face to face training on breathing exercise regimens in all three arms; high resistance IMT, low resistance IMT or usual care. The duration of the breathing exercises will be for a minimum of two weeks before the day of surgery. In some instances the surgery date may be cancelled or postponed; in such instances, the duration of treatment will be extended further until an alternative surgery date is confirmed. For non-cancer surgery (e.g. elective heart surgery), the waiting time between referral for surgery and surgery may be longer than 2 weeks; therefore, participants will be recruited as soon as feasible and may be required to perform the intervention for up to 8 weeks before the day of surgery.

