#### 2.1.3 Main study (Phase 2)

Progression criteria from Phase 1 to Phase 2:

- all centres participating in the pilot are recruiting (in one or more specialties);
- at least 40% of eligible patients are consenting to randomisation;
- each centre recruiting >8 patients/month (from any specialty);
- interventions are delivered according to the protocol in all centres;
- the allocated intervention is initiated in >=90% of randomised participants;
- >=70% of patients randomised to high resistance IMT or low IMT adhere to allocated interventions (adherence will be recorded electronically by the IMT device); we will define a patient as adherent with the intervention if they use the IMT device at least five days a week (for a minimum of 30 breaths per day).

If progression criteria are met, recruitment will continue at the Phase 1 hospitals and we will begin recruitment at a minimum of an additional two hospitals (depending on how recruitment is going in Phase 1). Delivery mode of the intervention will be based on the findings in Phase 1 and any amendments to the study will be submitted for approval by the regulatory authorities.

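### The SAP's non-adherent rule for IMT repeats the ≥ 30 breaths condition of the adherent rule, so every adherent participant also meets NO and some under-trainers are coded MISSING

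*SAP*

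**What the plan says.** In the SAP section on adherence to inspiratory muscle training, "The success of IMT will be defined by the adherence of participants to the intervention". The derived variable has three parts.

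- **YES:** at least one session on at least 5 days a week for at least 2 weeks, joined by "2 weeks after randomisation AND" to ≥ "30 breaths overall completed on each day".
- **Second list:** four alternatives joined by OR, the first three each ending "2 weeks after randomisation OR". Each of those three reverses one element of YES with a < sign (sessions, days per week, weeks). The fourth is again ≥ 30 breaths on each day. The NO label is absent from the text as supplied, but the list stands between YES and the residual category, so its role is clear.
- **Residual:** "MISSING: otherwise".

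The definition that this rule should implement is in the progression criteria. Protocol 5.2.6 says "we will define a patient as adherent with the intervention if they use the IMT device at least five days a week", and SAP 2.1.3 repeats it: "at least five days a week (for a minimum of 30 breaths per day".

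**The concern.** A YES/NO derivation should place each participant with data in exactly one category. Here the fourth NO item reverses nothing, so the adherent group lies wholly inside the non-adherent group. Participants whose only failing is too few breaths satisfy neither list and drop to MISSING, although their data exist and show non-adherence.

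Describing adherence is a stated aim of the pilot (SAP 2.1.1). The trial closed at the end of Phase 1 (SAP 1.1.2), so adherence is one of the results it can still deliver, and SAP 4.5.3 has it described by surgical specialty. If two programmers followed the printed rule, one could report no adherent participants and the other a sensible figure.

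**Working it through.** The plan states no figure to reproduce. The check is a truth table of the printed rule.

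**Inputs** (all from the SAP adherence rule):
- A: at least 1 session
- B: at least 5 days a week
- C: at least 2 weeks
- D: at least 30 breaths on each day

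**Rules as printed:**
- YES = A and B and C and D
- NO = (not A, B, C) or (A, not B, C) or (A, B, not C) or D
- MISSING = neither

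The sign-only correction replaces D by not D at the end of NO. The 16 combinations group as follows.

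| Failed among A, B, C | Combinations of A, B, C | D true, printed | D false, printed | D true, sign reversed | D false, sign reversed |
|---|---|---|---|---|---|
| none | 1 | YES and NO | MISSING | YES | NO |
| exactly one | 3 | NO | NO | NO | NO |
| two or three | 4 | NO | MISSING | MISSING | NO |

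**Printed rule:** both YES and NO, 1; NO only, 3 + 4 + 3 = 10; MISSING, 1 + 4 = 5; total 16. The single combination that satisfies YES is the one that is also NO, so the overlap covers all adherent participants. Of the 8 combinations with fewer than 30 breaths, 5 are MISSING and 3 are NO.

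**Sign reversed only:** YES, 1; NO, 3 + (1 + 3 + 4) = 11; MISSING, 4. The overlap is gone and all 8 combinations with too few breaths are NO. A participant with ≥ 30 breaths who fails two or more of A, B and C (for example, fewer than 5 days a week and fewer than 2 weeks) is now MISSING.

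**NO defined as data available and YES not met:** YES, 1; NO, 15; MISSING, 0.

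These are counts of logical patterns, not proportions of participants, and some patterns are unlikely in practice (no session but ≥ 30 breaths). Holding A true leaves 8 patterns. As printed, 1 is both, 5 are NO and 2 are MISSING. With the sign reversed, 1 is YES, 6 are NO and 1 is MISSING. The conclusion is the same.

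**Effect on the reported percentage.** Let N be the participants in the relevant population, all with device data, a the number truly adherent, and u the number wrongly coded MISSING. SAP 4.2 uses the total number of participants as denominator unless otherwise stated.
- NO applied last: adherent 0/N = 0%; coded NO, N − u.
- YES applied last: adherent a/N, which is correct; coded NO, N − a − u, against a true N − a.

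So the adherent percentage is either right or zero, depending on an order the SAP does not give. In the second case the non-adherent count is still too low by u.

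**The case against.** The strongest reply is that this is a one-character slip with an obvious intention. The other three NO items each reverse an element of YES, and Protocol 5.2.6 and SAP 2.1.3 state the intended definition, so a careful programmer would correct it. The SAP supplied is v0.3, and SAP section 7 requires sign-off of v1.0 before analysis. The use is also modest. Only the trial and SWAT primary outcomes are modelled (SAP 4.4.3), the adherence variable has no row in Tables A10 or A11, and the SWAT separately reports completion of 80% of sessions. All this limits the consequence. It does not make the rule correct, and the obvious repair still leaves a gap. A conversion fault is unlikely, because < survives in the three neighbouring items and the fourth carries an explicit ≥.

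A reader might also infer more than the documents support:

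- *That participants coded MISSING leave the denominator and inflate adherence.* SAP 4.2 keeps them in unless otherwise stated, and the adherence section states nothing else.
- *That a miscoded rate could wrongly pass the 70% progression criterion.* The funder confirmed closure (SAP 1.1.2), so no Phase 2 decision depends on it.
- *That per-protocol membership is corrupted.* SAP 3.3.2 lists failure to receive or adhere to the allocated intervention as a deviation, but does not cite this variable. Table A8 has its own non-adherence rows. The link is possible, not stated.
- *That counting from randomisation penalises a wait for training.* Protocol 6.4 says "The duration of the treatment commences when the participant receives face to face training". The SAP wording can be read as at least two weeks of training at some time after randomisation, and does not say the first two weeks. The SAP also follows protocol v3.0, whereas the protocol supplied is v2.0.

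**Conclusion.** The point holds as an error in an operative derivation rule. Followed literally, the rule puts every adherent participant in both categories. It codes as MISSING those who fail on breaths alone, and those with fewer than 30 breaths who also fail two or more of the session, day and week conditions. Those with fewer than 30 breaths who fail exactly one of these are still coded NO.

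The reach is limited to the descriptive adherence result and, if this variable supplies it, the count of per-protocol deviators. How many participants are affected cannot be known from the documents. The conclusion assumes that the unlabelled second list is the NO rule and that < 30 was intended; the position of the list and the two progression-criteria passages support both.

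**What to change.** In the SAP adherence section, keep the YES rule, define NO as device data available and YES not met (which includes fewer than 30 breaths on any required day), and reserve MISSING for absent device data. This removes the overlap and both gaps, and no order of evaluation is then needed. It would also help to say in SAP 3.3.2 whether this variable determines the adherence deviation. The cost is a few words in the SAP and one line of derivation code, before v1.0 is signed off. If analysis has already begun, SAP section 7 requires the change and its justification to be recorded in the final analysis report.

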#### 3.3.2 Per-protocol population

An analysis of the primary outcome on the per-protocol population will be considered if there are a considerable number of major protocol deviators (>5% of the ITT analysis population).

The following types of protocol deviation will be considered:

- Participant did not meet the study eligibility criteria but was treated in the study
- Participant did not receive/adhere to allocated intervention

Note, it may be possible for participants to be classified as a protocol deviation for more than one reason.

The frequency of each type of deviation will be tabulated by treatment allocation (see Table A8).

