#### 4.2 General calculations

Unless otherwise stated, all percentages will be calculated using the total number of participants from the relevant population as the denominator. For categorical and binary data, all percentages will be rounded to 2 decimal place(s), and for continuous measures, these will be summarised to one more decimal place than the data is collected, etc. P-values >0.001 will be summarised to 2 significant figures, and those <0.001 will be reported as <0.001.

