#### 4.5.3 Intervention

The intervention adherence will be described by surgical specialty (cardiac and non-cardiac surgery)

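### The SAP's IMT adherence rule contradicts itself: full trainers meet both YES and NO, and participants who fail only on breaths are coded MISSING instead of non-adherent

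*SAP*

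**What the plan says.** The derivation table under SAP 4.3.2 (Adherence to inspiratory muscle training) gives YES two parts. The first is at least one session on at least 5 days a week for at least 2 weeks after randomisation. The second, joined by AND, is at least "30 breaths overall completed on each day".

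The next list has four items. The first three each reverse one comparator (fewer than 1 session, fewer than 5 days, fewer than 2 weeks), and each ends in OR, for example "2 weeks after randomisation OR". The fourth is the 30-breath item again, still with the greater-than-or-equal sign. In the text available to us this list has lost its label, but it stands between YES and "MISSING: otherwise", so it can only be NO.

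Elsewhere the documents define adherence one way only. Protocol 5.2.6 and SAP 2.1.3 count a participant as adherent "if they use the IMT device at least five days a week (for a minimum of 30 breaths per day"), with use recorded electronically by the device. SAP 2.1.3 sets the Phase 1 target at no less than "70% of patients randomised to high resistance IMT or low IMT adhere to allocated interventions".

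Two further statements bear on the consequences. SAP 4.2 says that, unless otherwise stated, "all percentages will be calculated using the total number of participants from the relevant population as the denominator". SAP 4.5.3 keeps adherence among the reported results: "The intervention adherence will be described by surgical specialty".

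**The concern.** A derivation rule should put each participant in exactly one category. This one puts the fully adherent in two and some of the non-adherent in none. It cannot be programmed as written: someone must decide whether YES or NO takes precedence, and the SAP does not say.

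The group that falls through is not far-fetched. Protocol 5.6.3.2 lets high-resistance participants do as many breaths as they can tolerate, up to 30 per session, and allows the starting load to be set at what is tolerable for at least 20 breaths. Someone who does one 20-breath session a day satisfies the session condition and fails the breath condition.

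At stake is a result that survives early closure. Describing adherence is a Phase 1 objective (SAP 2.1.1), the derivation table calls adherence the measure of success of IMT, and SAP 4.5.3 still reports it. Non-adherence is also listed as a deviation type in SAP 3.3.2 ("Participant did not receive/adhere to allocated intervention"), where deviations in more than 5% of the ITT population would prompt consideration of a per-protocol analysis.

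**Working it through.** No sample size or power figure depends on this rule, and the plan states no figure to reproduce. The check is a truth table, followed by a small illustration.

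**Inputs** (derivation table, SAP 4.3.2). A: at least 1 session. B: at least 5 days a week. C: at least 2 weeks. D: at least 30 breaths on each day. Each NO item is read as the YES conditions with one comparator reversed.

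- YES = A and B and C and D
- NO as printed = (not A, B, C) or (A, not B, C) or (A, B, not C) or D
- MISSING = neither

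**All 16 combinations, grouped**

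| Breaths | Failures among A, B, C | Cells | As printed | Only the last sign reversed | Any YES condition failed = NO |
|---|---|---|---|---|---|
| 30 or more | none | 1 | YES and NO | YES | YES |
| 30 or more | exactly one | 3 | NO | NO | NO |
| 30 or more | two or more | 4 | NO | MISSING | NO |
| under 30 | none | 1 | MISSING | NO | NO |
| under 30 | exactly one | 3 | NO | NO | NO |
| under 30 | two or more | 4 | MISSING | NO | NO |

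As printed, one cell is in both categories and 1 + 4 = 5 cells are MISSING, all with fewer than 30 breaths. Reversing only the last inequality removes the overlap and rescues those 5 cells, but sends 4 others to MISSING: those with 30 or more breaths that fail two or more of the other conditions (for example, fewer than 5 days a week and fewer than 2 weeks). Not every cell is attainable in practice. A looser reading of the session, day and week items could also catch some multiple failures as NO. Neither point affects the two rows with no failure among A, B and C.

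**Effect on the reported result.** The documents give no adherence data, so the shares are assumed: 60% meet all conditions, 15% fail only on breaths, 25% fail otherwise and are coded NO. True adherence is 60% and true non-adherence is 15 + 25 = 40%.

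| Coding choice | Adherent | NO, share of all | MISSING, share of all |
|---|---|---|---|
| YES first, MISSING kept in the denominator (SAP 4.2) | 60/100 = 60% | 25% | 15% |
| YES first, MISSING dropped | 60/(100 − 15) = 70.6% | 25% | 15% (excluded from the rate) |
| NO first | 0% | 60 + 25 = 85% | 15% |

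**Range for the second row.** Reported rate = true rate / (1 − share failing only on breaths). For true rates of 50% to 70% and shares of 5% to 25%, it runs from 0.50/0.95 = 52.6% to 0.70/0.75 = 93.3%.

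**The case against.** The strongest reply is that this is a plain drafting slip with little consequence. The intended meaning is clear from protocol 5.2.6 and SAP 2.1.3, a 0% result would be noticed at first output, and the SAP supplied is marked v0.3, with section 7 requiring v1.0 to be signed off before analysis. All of that is fair, and it limits the weight of the point. It does not make the printed rule usable, and the obvious one-sign repair leaves a second gap.

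A reader might infer several stronger things that the documents do not support.

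- **That the rule inflates adherence.** This needs YES to take precedence and MISSING participants to leave the denominator. SAP 4.2 keeps them in unless otherwise stated, and the adherence table states no exception. Under that default the adherent percentage is correct with YES first; only NO and MISSING are wrong.
- **That it carries the trial over its 70% criterion.** The 70.6% above rests on assumed shares and on dropping MISSING. SAP 1.1.2 records that the funder confirmed closure in May 2022, so the criterion no longer decides whether Phase 2 goes ahead.
- **That everyone below 30 breaths becomes MISSING.** Those who also fail exactly one session, day or week condition are still coded NO.
- **That the per-protocol trigger is distorted.** SAP 3.3.2 does not cite this variable, and Table A8 has its own deviation rows, none with a 30-breath limit. The link is possible but not stated.

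**Conclusion.** The rule is wrong as written. It contradicts itself and conflicts with the adherence definition in protocol 5.2.6 and SAP 2.1.3. The other less-than signs in the same cell came through intact, so a sign lost in reading the PDF is unlikely, though it cannot be excluded.

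What is certain is that the NO and MISSING counts are misallocated and that the adherence rate is indeterminate until a coding order is chosen: the true rate, a higher one, or 0%. The size of any misallocation depends on how many participants fall below 30 breaths, which the documents do not show.

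The reach is limited to the descriptive adherence result and, only if this variable is used there, the deviator count. The primary PPC comparison is by intention to treat and does not use it. The point should be settled before programming, but it does not threaten the trial's main conclusion.

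**What to change.** In the SAP adherence table:

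1. Leave YES as it is.
2. Define NO as device data available and any YES condition not met. This replaces the four-item list, closes the gap that a one-sign correction would leave, and brings the table into line with protocol 5.2.6 and SAP 2.1.3.
3. Reserve MISSING for participants with no device data.
4. State the denominator: all participants randomised to high or low resistance IMT, consistent with SAP 4.2, with the number missing shown beside the percentage.
5. Say in SAP 3.3.2 whether this variable determines non-adherence as a protocol deviation.

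The cost is a few lines of SAP text and one line of code, with no new data. It can go into v1.0 before sign-off; if analysis has already begun, section 7 of the SAP requires the change and its reason to be recorded in the final analysis report.

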#### Success of participant blinding using the Bang Blinding Index

The success of participant blinding will be inferred from blinding indices.

New variable	Rules
Blinding indices	Blinding indices will be calculated using the method proposed by Bang et al.

## 4.4 Analysis of the outcomes

#### 4.4.1 First stage to the analysis

There are insufficient data to support any statistical basis for combining the usual care and low IMT groups as planned, therefore the planned first stage of analysis comparing low resistance IMT and usual care groups will not be performed. Instead, the primary and secondary outcome data will be described by the three groups separately, as well as the combined low resistance IMT/usual care group. The primary analysis of the study will compare the high resistance IMT

group with the combined low IMT/usual care groups as the hypothesis was that the low resistance IMT would not differ to usual case and the sample size per group was set on that basis.

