device. In contrast to the high resistance group, the low resistance IMT group will not be encouraged to adopt a specific breathing pattern. Instead they will be guided on how to breathe gently through the device in a manner that will minimise the risk of hypocapnia and avoid any training stimulus to the inspiratory muscles. Participants will be asked to complete the paper training diary and rate their perceived exertion (using the RPE rating scale). They will watch a modified version of the training video (with the sessions on how to increase load on the device removed) during the face-to-face meeting and will be given written instructions to take home with them.

The low resistance loading regimen (10% MIP) gives a perceptible and convincing training stimulus from the participant perspective, but this stimulus is not expected to cause a change in the physiological outcomes (change in MIP from baseline) [26]. It can be set and locked at a constant training load to prevent participants in the low resistance IMT group from manipulating it. The low resistance training regimen poses no risk to participants, but substantially improves the validity of the study for the following reasons:

- i) Assuming adequate blinding, it allows the efficacy of high resistance IMT to be estimated, i.e. excluding any placebo effect of the IMT intervention;
- ii) There is a theoretical possibility of contamination (participants obtaining a device and performing IMT on their own) or health behavioural change in the usual care group because of lack of blinding (although experience suggests that this is rare), therefore a comparison of IMT vs. usual care may result in a biased estimate.

We will not differentiate between high resistance IMT and low resistance IMT when describing the study to participants in the patient information materials, i.e. participants will be told they will be randomised to different types of breathing exercises either with or without a device.

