## 4. Statistical analyses and report content

#### 4.1 General considerations

The statistical analysis is the responsibility of the BTC study statisticians.

Where interventions are being compared formally using statistical modelling, the usual care and low-resistance IMT groups combined will act as the reference category (see section for 4.4.1 for discussion of initial analysis).

All statistical tests will be superiority comparisons; they will be 2-sided and will be performed using a 5% significance level, with the exception of tests for interactions that will be performed using a 10% significance level.

No formal adjustment will be made for multiple testing, but consideration will be taken in interpretation of results to reflect the number of statistical tests performed and the consistency, magnitude and direction of treatment estimates for different outcomes.

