#### 4.4.3 Analysis models

General methods of presentation and assessing treatment effects for all outcomes are outlined below according to data type. As the trial was halted early, only the primary outcome of the trial and the primary outcome of the SWAT will be formerly modelled. The secondary outcomes will be tabulated by treatment group but will not be modelled (i.e. the difference between groups will not be quantified). The secondary outcomes of the SWAT will be tabulated following the 2x2 factorial design groups.

Data type	Outcomes					
Binary	Proportion of participants with any PPC					
Continuous	
 
Load (SWAT outcome)
 
					

Each data type will be summarised and compared between the groups according to the following:

- Binary outcomes will be presented as numbers and percentages of participants in each treatment group. Outcomes will be compared between treatment groups using generalised linear models, with treatment comparison estimates presented as adjusted risk ratios (RR) and risk differences (RD) with 95% CIs.
- Continuous outcomes will be summarised as means and SDs (or medians and IQRs if distributions are skewed). Outcomes will be compared using linear mixed effects methodology with treatment groups and study design variables, and patient terms fitted as random effects. A follow-up x load adjustment method interaction will be fitted; if this is not statistically significant at the 10% level overall treatment effects for follow-up and adjustment method will be reported. If the interaction is statistically significant differences in load between adjustment methods with and without follow-up will be described.

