## Statistical Analysis Plan Inspire IRAS Ref: 250345

Non-invasive ventilation (including continuous positive airway pressure (CPAP) and/or pressure support (BIPAP))

support (BIPAP))		
Optiflow (highflownasaloxygentherapy) Prophylactically to prevent a pulmonary complication	-	-
For treatment of a pulmonary complication	-	-
Length of ICU stay	-	-
Length of hospital stay	-	-
Antibiotic prescription	-	-
Bronchodilator prescription	-	-
Change in maximal inspiratory pressure (MIP)	-	-
Change in Spirometry (forced expiratory volume, FEV1 and forced vital capacity, FVC) measurements	-	-
Progression in training load		
In-hospital mortality	-	-
30-day mortality	-	-
Patient questionnaires at 3 months	-	-
Patient questionnaires at 6 months	-	-

\* Effect estimate is from model comparing high resistance IMT to the sham IMT and usual care groups combined

Table A12: PPC and progression in training load, within surgical specialty and ARISCAT score

Outcome	Randomised to IMT (n=xx)	Randomised to Sham IMT/Usual care (n=xx)
By surgical specialty		
Any PPC		
Cardiac (n=XXX)		
Non-cardiac (n=XXX)		
Progression in training load		
Cardiac (n=XXX)		
Non-cardiac (n=XXX)		
By ARISCAT score		
Any PPC		
Score 24-44 (n=XXX)		
Score ≥45 (n=XXX)		
Progression in training load		
Score 24-44 (n=XXX)		
Score ≥45 (n=XXX)		

Table A13: Adverse events and serious adverse events during index hospital admission

	Randor	mised Pa	tients (N=XXX	()		F	Relatedness (S	AEs)			Intensity (SAI	Es)
	AEs		SAEs							Una	anticipated eve	nts only
	Events/ Patients	% 	Events/ Patients	% 	Not related	Unlikely to be related	Possibly related	Probably related	Definitely related	Mild	Moderate	Severe
Any anticipated event												
Infective												
Viral Infection												
Pneumonia												
Respiratory infection												
Cardiovascular												
GI												
Respiratory/pulmonary												
Nervous system / Neurological / Psychiatric												
Immune system												
Metabolism / Nutrition												
Eye												

	Randor	nised Pa	tients (N=XXX	.)		R	elatedness (S	AEs)		Intensity (SAEs)		
	AEs		SAEs							Una	nticipated ever	nts only
	Events/ Patients	% 	Events/ Patients	% 	Not related	Unlikely to be related	Possibly related	Probably related	Definitely related	Mild	Moderate	Severe
Ear / Labyrinth												
Hepatobiliary												
Renal / Urinary												
Reproductive / Breast												

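### Pooling low resistance IMT with usual care is now an untested assumption, and no adjusted estimate is planned for high v low resistance, the only participant-blinded contrast

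*SAP*

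**What the plan says.** Protocol 7.1.2 names high resistance IMT v combined low resistance IMT and usual care as the expected primary comparison, and the 2:1:1 allocation was chosen for it. Pooling was subject to a first-stage comparison of the two control arms. If low resistance IMT did better than usual care by more than 0.25 SD, the primary analysis would switch to high v low resistance, so that including usual care did not inflate the benefit. If the arms were similar, or usual care did better, they would be pooled.

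Protocol 5.6.4.1 gives a reason for the low resistance arm: with adequate blinding, "it allows the efficacy of high resistance IMT to be estimated, i.e. excluding any placebo effect of the IMT intervention". The same section warns that comparing IMT with unblinded usual care may be biased. Participants are blinded only between high and low resistance (Protocol 5.4 and 6.2).

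SAP 4.4.1, written after early closure, removes the first stage because "There are insufficient data to support any statistical basis for combining the usual care and low IMT groups as planned". The primary analysis then compares high resistance IMT "with the combined low IMT/usual care groups as the hypothesis was that the low resistance IMT would not differ to usual" care, with group sizes set on that basis. Outcomes are still tabulated: "the primary and secondary outcome data will be described by the three groups separately, as well as the combined low resistance IMT/usual care group".

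For formal models, SAP 4.1 says "the usual care and low-resistance IMT groups combined will act as the reference category". SAP 4.4.3 says "only the primary outcome of the trial and the primary outcome of the SWAT will be formerly modelled"; secondary outcomes "will not be modelled (i.e. the difference between groups will not be quantified". Table A11 has one effect column, with the footnote "Effect estimate is from model comparing high resistance IMT to the sham IMT and usual care groups combined".

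**The concern.** The protocol identified a specific bias (a placebo or behavioural effect separating the sham arm from usual care) and gave a safeguard against it: check first, then switch to high v low resistance if needed. The SAP removes the safeguard and puts no supportive contrast in its place. Half of the planned comparator is now the group whose participants know they have no device.

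At stake is how the one reported effect can be read. If low resistance IMT and usual care differ, the pooled estimate mixes the specific effect of training with part of that difference, and no planned model output shows it. The contrast for which the low resistance arm was partly created gets counts but no adjusted risk ratio, risk difference or interval.

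**Working it through.** **1. Reproducing the plan's figures.** Inputs (SAP 2.4.1, SAP 4.1): 20% v 15%, two-sided 5%, 90% power, groups of 1250, 625 and 625.
- Per arm without continuity correction: [1.96·√(2 × 0.175 × 0.825) + 1.2816·√(0.15 × 0.85 + 0.20 × 0.80)]² / 0.05² = 1212.
- With continuity correction: 1252 per arm, 2504 in total. Stated: 2500.
- Power for high v low resistance, 1250 v 625, with continuity correction: 75.4% for 15% v 20% and 89.6% for 14% v 20%. Stated: 75% and 90%.
- Low resistance v usual care, 625 v 625 at 20%: 1.96·√(2 × 0.16/625) = 4.4 points. Stated: 4.5.

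The design figures hold.

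**2. What the pooled contrast estimates.** Write pH, pL and pU for the PPC risks under high resistance, low resistance and usual care. With equal control arms:

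pH − (pL + pU)/2 = (pH − pL) − (pU − pL)/2

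So half of the low v usual care difference enters the pooled risk difference. Illustration, with rates assumed:
- pH = 15%, pL = 15%, pU = 20%: pooled difference 15 − 17.5 = −2.5 points; high v low = 0.
- pH = 15%, pL = 17.5%, pU = 20%: pooled difference 15 − 18.75 = −3.75 points; high v low = −2.5.
- pH = 15%, pL = pU = 20%: both differences are −5 points, so pooling does no harm.

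**3. Precision at a reduced N.** The SAP gives no actual number recruited. About 321 is the Phase 1 projection (SAP 2.1), and SAP 1.1.2 says recruitment was slower than planned, so N is an assumption and a range is shown. Allocation 2:1:1, 15% with high resistance, 20% in each control arm. Wald 95% half-widths:
- High v pooled: 1.96·√(0.1275/(N/2) + 0.16/(N/2))
- High v low: 1.96·√(0.1275/(N/2) + 0.16/(N/4))
- Low v usual care: 1.96·√(2 × 0.16/(N/4))

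| Assumed N | High v pooled | High v low | Low v usual care |
|---|---|---|---|
| 160 | 11.7 points | 14.7 points | 17.5 points |
| 321 | 8.3 points | 10.3 points | 12.4 points |
| 640 | 5.9 points | 7.3 points | 8.8 points |

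At N = 321: √(0.1275/160.5 + 0.16/80.25) × 1.96 = 10.3 points and √(0.2875/160.5) × 1.96 = 8.3 points. The ratio is √(0.4475/0.2875) = 1.25 at any N. Power at N = 321 for 15% v 20% is 22% for high v pooled and 17% for high v low.

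The last column supports the SAP's statement that the data cannot settle whether pooling is justified. The first two show that imprecision alone does not explain modelling one contrast and leaving out the other.

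**The case against.** A reader might infer that SAP 4.4.1 contradicts itself by denying a basis for pooling and then pooling. The text does not support that. What is lacking is the data-driven basis foreseen in the protocol; the section goes on to give a prior one, the design hypothesis and the group sizes built on it. Pooling was also the protocol's expected primary comparison, and two of the three branches in 7.1.2 lead to it. Where pooling applied, 7.1.2 listed no extra high v low estimate, although the sample size section quotes power for one.

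Dropping the check is defensible. At N = 321 it would carry ±12.4 points. The rule was also unclear: 7.1.2 speaks of the primary outcome and then of 0.25 SD in MIP. On a 20% binary outcome 0.25 SD would be 0.25 × √(0.2 × 0.8) = 10 points, less than that half-width.

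Two other stronger readings also fail. The high v low comparison is not hidden: Table A11 has separate sham and usual care columns, so a crude difference can be derived. Nor does all of any placebo effect enter the estimate; with equal control arms half does. Blinding of clinical staff and assessors, PPC criteria kept as objective as possible, and a leaflet given to every arm limit it further.

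What stands is that a conditional safeguard has become an unconditional assumption, and that the participant-blinded contrast has no planned adjusted estimate.

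**Conclusion.** The point holds as a gap in the planned estimates, not as an error in the choice of primary analysis. High v pooled can stay primary, but it measures the specific effect of training only if low resistance IMT equals usual care, and the trial cannot test that at its reduced size. The possible distortion is half of whatever difference exists between the control arms: 2.5 points under an assumed 5-point difference, which is as large as the trial's whole target effect and so a demanding illustration.

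The high v low interval would be about 1.25 times as wide as the pooled one under 2:1:1 allocation and 15% v 20%. Both are imprecise over the assumed range of N, so neither is likely to settle the clinical question; the gain is in interpretation. The SAP says it follows protocol v3.0, and the protocol available is v2.0, so any later change to 7.1.2 could not be checked.

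**What to change.** - **SAP 4.4.3:** keep the two-group high v pooled model as primary. Add a separate supportive model of any PPC, with the same adjustment for stratification factors, giving the risk ratio and risk difference with 95% CI for high v low resistance. High v usual care is optional. Label these supportive and imprecise. A single three-level model should not replace the primary one, because it does not directly give the pooled risk ratio.
- **SAP 4.1:** allow low resistance IMT (and usual care, if used) as the reference category in the supportive model.
- **Table A11:** add the matching effect column or columns; the separate control columns already exist.
- **SAP 4.4.1:** state that the pooled result assumes low resistance IMT equals usual care and that this assumption was not tested.

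The cost is a few lines of text and code, and one or two more wide intervals to interpret. The SAP is marked v0.3, and its section 7 allows documented changes before analysis, so the estimate can be prespecified if analysis has not begun.
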